3.3.2 Blinding

This is an open-label study.

3.3.3 Treatment compliance

Records of study medications used, and dosages administered, will be kept during the study. The study monitor will note drug accountability during site visits and at the completion of the study.

3.4 On Study Evaluation

During the treatment phase, patients will be monitored according to the Assessments delineated below:

3.4.1 Assessment prior to each dose of MDX-010

3.4.1.1. Physical examination

3.4.1.2. Assessment of performance status

3.4.1.3. Hematology (Hemoglobin, Hematocrit, Complete blood cell count with differential and platelet count (direct), and biochemistry testing (Albumin, Alkaline phosphatase, ALT, AST, Bilirubin (total and direct), Calcium Chloride, Bicarbonate, Creatinine, Glucose, Lactate dehydrogenase (LDH), Potassium, Sodium, Total protein, Urea nitrogen (BUN), Uric acid). A urine pregnancy test will be performed and confirmed negative prior to each dose.

3.4.1.4. Blood pressure (systolic and diastolic), pulse rate, temperature and respiratory rate at baseline for each dose, then every 30 minutes throughout the MDX-010 infusion, and for one hour after infusion, and then routinely unless otherwise indicated.

3.4.1.5. Assessment of adverse events

3.4.1.6. Assessment of concomitant medications

3.4.2 Assessment prior to each new course

3.4.2.1. Physical examination

3.4.2.2. Assessment of performance status

3.4.2.3. Diagnostic imaging appropriate to tumor evaluation, using the same imaging modality, method of assessment, or technique used for baseline evaluation. Repeat diagnostic imaging will be performed after each course of therapy (approximately day 55).

3.4.2.4. Ophthalmologic examination at the completion of course 1 and again if any ocular symptoms develop, including retinal pigmentation changes. Visual acuity will be performed during each assessment.

3.4.2.5. Autoimmune Panel:

Antithyroglobulin antibody

ANA, if positive perform the ENA, if ENA positive, perform the following tests (If negative, then a sample of serum will be stored for subsequent testing in the event that the ANA becomes positive at a later date):

- Anti-phospholipid antibody
- Anti-neutrophil cytoplasm antibody
- CH50
- Anti-DNA antibody
- Anti-SSA antibody
- Anti-SSB antibody
- Rheumatoid factor (RF)

3.4.2.6. Thyroid function tests, as defined for baseline in Section 2.2.12.

3.4.2.7. Hematology (Hemoglobin, Hematocrit, Complete blood cell count with differential and platelet count (direct) and sedimentation rate, and biochemistry testing (Albumin, Alkaline phosphatase, ALT, AST, Bilirubin (total and direct), Calcium Chloride, Bicarbonate, Creatinine, Glucose, Lactate dehydrogenase (LDH), Potassium, Sodium, Total protein, Urea nitrogen (BUN), Uric acid)

3.4.2.8. Pulmonary function tests will be conducted if patients develop any clinical sign or symptom suggestive of deterioration of pulmonary function.

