2.2.13 Biochemistry

In this study, patients will receive 3 mg/kg MDX-010 antibody intravenously every three weeks. Our experience with MDX-010 in patients with melanoma or renal cell cancer has shown a correlation between severe autoimmunity and tumor response. It has also shown a higher rate of both autoimmune toxicity and tumor response when MDX-010 is administered at repeated doses of 3 mg/kg. Two separate groups of 21-41 patients will be treated with intravenous infusion of MDX-010 at 3mg/kg for all doses. One of the groups will have locally advanced disease, while the other group will have distant metastases. The two groups will be evaluated separately using the same single arm, two-stage phase II design described in Section 5.5.

Four doses will be designated as a course of therapy and evaluations will be conducted at the end of each course, 3 weeks after the 4th infusion. An informal interim evaluation may be performed 3 weeks after the 2nd infusion to rule out rapid disease progression, but the formal evaluation with tumor measurements will be performed approximately 3 weeks after the 4th dose. CT scanning may be performed at any time during protocol implementation in the event that there is clinical evidence of disease progression

Treatment will be limited to 2 courses of therapy. Patients that respond and subsequently relapse will be treated with additional courses of therapy. Patients may come off study at any time if rapid disease progression occurs.

Patients in the locally advanced disease cohort may experience sufficient tumor response that their disease is rendered resectable. If this occurs, these patients will be treated with standard pancreatic resection rendering them NED (no evidence of disease).

3.2 Drug Administration:

MDX-010: All MDX-010 doses will be administered as an intravenous infusion controlled by an infusion pump. For administration, MDX-010 is to be injected into the IV bag and diluted in 0.9% Normal Saline, USP, to a concentration between 0.2 mg/ml and 1 mg/ml as specified in Section 8.1, and should be administered over 90 minutes through an add-on filter set with 1.2 µm air-eliminating filter [REDACTED]

Do not administer as an i.v. push or bolus. If \geq Grade 3 bronchospasm or other hypersensitivity reaction occurs, the infusion should be discontinued and no additional MDX-010 should be administered.

Surgical guidelines

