Medarex reserves the right to discontinue any study for administrative reasons at any time. If appropriate, reimbursement for reasonable expenses will be made. Authorized physicians must notify ORKAND when a patient is taken off study.

3.7 Post Study Evaluation (Follow up):

Patients will undergo physical examination, including vital signs, blood sampling for hematological and biochemical evaluation and, as clinically indicated, chest radiography, pulmonary function, diagnostic imaging, three weeks following the last treatment, then at three month intervals for 1 year, at 6 month intervals for two years, and then at 12 month intervals or until disease progresses. Prior to termination of participation in the study, each patient will undergo physical examination, diagnostic imaging, and blood sampling for hematological, biochemical, and immune function assessments.

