5.3.1.4 Confirmatory Measurement/Duration of Response

Confirmation

To be assigned a status of PR or CR, changes in tumor measurements must be confirmed by repeat studies that should be performed at least 4 weeks after the criteria for response are first met. In the case of SD, follow-up measurements must have met the SD criteria at least once after study entry at a minimum interval of 6-8 weeks.

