5.3.1.5 Duration of overall response

The duration of overall response is measured from the time measurement criteria are met for CR/PR (whichever is first recorded) until the first date that recurrent or progressive disease is objectively documented (taking as reference for progressive disease the smallest measurements recorded since the treatment started).

The duration of overall complete response is measured from the time measurement criteria are first met for CR until the first date that recurrent disease is objectively documented.

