2.3.3 Treatment Phase /Retreatment Cycle

Four doses will be designated as a course of therapy and evaluations will be conducted at the end of each course, three weeks after the 4th infusion. An informal interim evaluation may be performed three weeks after the 2nd infusion to rule out rapid disease progression, but the formal evaluation with tumor measurements will be performed approximately three weeks after the 4th dose. CT scanning may be performed at any time during protocol implementation in the event that there is clinical evidence of disease progression. A second course of treatment may be offered to subjects with progressive disease who tolerate the first course of treatment and are willing to undergo a second course of treatment with ipilimumab rather than pursue an alternate therapy at that time. Treatment will be limited to 2 courses of therapy. Subjects that respond (PR or CR) and subsequently relapse will be treated with up to 2 additional courses of therapy. Subjects may come off study at any time if rapid disease progression occurs. Subjects in the locally advanced disease group may experience sufficient

tumor response that their disease is rendered resectable. If this occurs, these subjects will be treated with standard pancreatic resection rendering them NED (no evidence of disease).

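### Protocol 3.4.2.3 puts the end-of-course response scan at about day 55, eight days before the course's fourth dose

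*Protocol*

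**What the plan says.** - **Protocol 3.4.2.3**, under the assessments made before each new course: "Repeat diagnostic imaging will be performed after each course of therapy (approximately day 55" (the bracket closes there).
- **Protocol study design text** (section 3.1 by the table of contents; in the available text it follows heading 2.2.13). Dosing is three-weekly and four doses make a course. Then: "evaluations will be conducted at the end of each course, 3 weeks after the 4th infusion", and again: "the formal evaluation with tumor measurements will be performed approximately 3 weeks after the 4th dose". An earlier look is optional: "An informal interim evaluation may be performed 3 weeks after the 2nd infusion to rule out rapid disease progression".
- **Protocol schedule table.** The first four infusions are marked at Days 0, 21, 42 and 63, the last three with a ±2-day window. The first on-study marks for diagnostic imaging and Disease Response are at Day 84 ±2. No imaging is marked from Day 0 to Day 63. The next imaging mark is at Day 105 ±4, without a Disease Response mark.
- **Protocol 3.3.1** lets doses within a course be delayed by up to 3 weeks while an autoimmune toxicity resolves.
- **Protocol 5.3.1.4 and 5.3.1.5.** A PR or CR "must be confirmed by repeat studies that should be performed at least 4 weeks after the criteria for response are first met". Duration of response is "measured from the time measurement criteria are met for CR/PR (whichever is first recorded" in the record.
- **SAP 2.3.3:** "the formal evaluation with tumor measurements will be performed approximately three weeks after the 4th dose". SAP Table 1 places an evaluation, and SAP Table 2 places imaging and Disease Response, at Day 84 ±2.

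**The concern.** The sentence gives two times for one scan that cannot both be right. Its words put the scan after the course; its day number puts it inside the course, between doses 3 and 4. A site working from the day number would make its end-of-course assessment on three doses, while a site working from the words or the schedule would make it on four.

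This scan is one of those used to judge PR and CR, the primary endpoint. Because 5.3.1.5 starts the response clock when the criteria are first met, the two readings could also give different start dates for the same response.

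**Working it through.** **Inputs.** Dosing interval 21 days and four doses per course (study design text); visit windows (schedule table); disputed day 55 (3.4.2.3); maximum delay 3 weeks (3.3.1).

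**1. Dose days.** Dose k falls on day 21 × (k − 1), which gives Days 0, 21, 42 and 63. These match the infusion marks in the protocol schedule.

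**2. Formal evaluation.** Dose 4 plus 3 weeks: 63 + 21 = Day 84. This reproduces the schedule's Day 84 ±2 and the SAP's Day 84 ±2.

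**3. Position of day 55.**

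| Comparison | Nominal | With ±2-day window |
|---|---|---|
| After dose 3 (Day 42) | 55 − 42 = 13 days | 55 − 44 = 11 to 55 − 40 = 15 |
| Before dose 4 (Day 63) | 63 − 55 = 8 days | 61 − 55 = 6 to 65 − 55 = 10 |
| Before the formal evaluation (Day 84) | 84 − 55 = 29 days | 82 − 55 = 27 to 86 − 55 = 31 |

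**4. Readings that might explain day 55.**
- Optional look 3 weeks after dose 2: 21 + 21 = Day 42. No match.
- Three weeks after dose 3: 42 + 21 = Day 63. No match.
- Counted from the start of course 2. The SAP schedule marks an infusion at Day 84 and the protocol schedule marks one at Day 105, so both starts were tried. From Day 84: 84 + 55 = 139, against dose 4 at 84 + 63 = 147. From Day 105: 105 + 55 = 160, against 105 + 63 = 168. Day 55 is 8 days before dose 4 in both.
- Delayed dosing. If dose 4 slips by 3 weeks to 63 + 21 = Day 84, day 55 is 84 − 55 = 29 days before it. Delay widens the gap.
- The stable-disease interval of 6-8 weeks in 5.3.1.4 is 42 to 56 days and does contain 55. It is a minimum interval for calling SD, not a scan date, and does not place day 55 after a four-dose course.
- Approximation. The on-study windows are ±2 to ±4 days, so the qualifier cannot cover 29 days.

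No reading recovers day 55.

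**5. Check on confirmation.** The gap from Day 84 ±2 to Day 105 ±4 is 105 − 84 = 21 days, ranging from 101 − 86 = 15 to 109 − 82 = 27. All are below the 28-day minimum, so the Day 105 scan cannot confirm a response first seen at Day 84. Later scans can:
- End of course 2: 84 + 63 + 21 = Day 168 or 105 + 63 + 21 = Day 189, which is 84 or 105 days later.
- First 3-month follow-up, taking 3 months as 91 days (an assumption): 63 + 91 = Day 154 if counted from the last dose, or 84 + 91 = Day 175 if counted from the 3-week visit, which is 70 or 91 days later.

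**The case against.** **It is an editorial slip.** One bracketed day number stands against the rest of its own sentence, the subsection's heading, two statements in the study design text and the schedule. Most readers would go to Day 84. This stands as a limit on the size of the problem. It does not remove it: the number is an operative instruction, and it is the only calendar day that 3.4.2.3 gives.

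**The SAP is weak support.** It cites a protocol section 2.2.7 C and describes PK and HAHA sampling, none of which is found in the March 2005 protocol text, so it may follow a later version that had already corrected the day. This stands. The contradiction is shown from the protocol alone.

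**A fixed Day 84 would fail too.** With the delay allowed in 3.3.1, dose 4 could fall on Day 84 and the evaluation on 84 + 21 = Day 105. This also stands, and the correction must be tied to the dose.

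**Stronger readings that the documents do not support.** A reader might infer that the primary endpoint and the stage-1 rule (0-1 versus 2 or more of 21) hang on this one scan. They do not: 5.3.1.3 takes the best response from the start of treatment until progression, 5.3.1.4 requires confirmation, and the schedule still marks Day 84 imaging even where a site also scans at day 55. A reader might also infer from step 5 that a response could not be confirmed. But 5.3.1.4 already mandates the repeat study, later scans can supply it, and no passage makes Day 105 the confirmation scan.

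**Conclusion.** The point holds as an internal inconsistency in the protocol. Under nominal dosing, day 55 falls after three doses and 8 days (6 to 10) before the fourth. A first response could be dated about 29 days early (27 to 31) relative to the formal evaluation. This rests only on the three-week interval, the four-dose course and the visit windows.

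The consequence for this trial is small. SAP 5.10 reports no clinical response in the first stage, and SAP 5.8 states that no efficacy analysis will be done. It would be tempting to conclude that the early day cost the trial a response or power. Nothing in the documents shows which day sites used or that any response was missed, and no loss of power can be derived from them.

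One side note remains. Protocol 3.7 lists follow-up imaging among tests done "as clinically indicated, chest radiography, pulmonary function, diagnostic imaging, three weeks following the last treatment" and at later intervals, while the schedule marks it at follow-up without that condition. The conflict with 5.3.1.4 is at most indirect, since that section does not mention follow-up visits and 3.7 itself requires imaging before participation ends.

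**What to change.** In 3.4.2.3, replace the bracketed day with *approximately 3 weeks after the 4th dose of that course*, and note that this is nominally Day 84 in course 1 when no dose is delayed. This takes the timing from the study design text, applies to every course and remains correct under the delays in 3.3.1. A bare Day 84 ±2 would not.

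Optionally, reconcile the conditional follow-up imaging in 3.7 with the unconditional mark in the schedule.

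The cost is one phrase, plus one clause if the side note is taken up. No scan is added, no dose or treatment rule changes, and the SAP needs no edit. If a later protocol version exists, check first whether it already corrects the day.

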3.4.2.9. PBMC (peripheral blood mononuclear cells) sample

Peripheral blood mononuclear cells (PBMC) will be isolated and purified from samples obtained at baseline and after every course, by drawing 75 ml of blood at these times according to the schedule. In addition, 5 ml of serum will be obtained and stored at baseline and at the time of each blood draw.

Schedule								
	On-Study Evaluation						Follow up	
Visit	2	3	4	5	6	7 ⁷		
Day	0	21 ±2d	42 ±2d	63 ±2d	84 ±2d	105 ±4d		Variable ¹
MDX-010 Dose (mg/kg)	3	3	3	3	3	3		
Adverse events	X	X	X	X	X	X		X
	X	X	X	X	X	X		X
Physical examination	X	X	X	X	X	X		X
Assessment for ocular symptoms	X	X	X	X	X	X		X
Vital signs ³	X	X	X	X	X	X		X
Performance Status	X	X	X	X	X	X		X
Ophthalmologic examination**					X			
Pulmonary Function Testing ²								
Diagnostic imaging					X	X		X
Hematology		X	X	X	X			X
Biochemistry		X	X	X	X	X		X
Urinalysis					X			
Urine pregnancy test ⁴	X	X	X	X		X		
ANA ⁵					X			
Antithyroglobulin					X			
Thyroid Function Test ⁶					X			
Blood sample					X			
Infusion of MDX-010	X	X	X	X		X		
Disease Response					X			X

- ¹ 3-month intervals for 1 year, 6-month intervals for 2 years, and 12-month intervals until recurrence of disease
 - ² •²PFT's will be performed if patients develop any clinical sign or symptom suggestive of deterioration of pulmonary function.
 - ³ Vital signs will be monitored every 30 minutes for the duration of the MDX-010 infusion and for one hour following infusion completion, and then routinely unless otherwise indicated.
 - ⁴ A negative urine pregnancy test will be confirmed prior to each dose of MDX-010 in women of child-bearing potential.
 - ⁵ If ANA positive, perform the ENA. If ENA positive, perform the tests indicated in Section 3.4.2.5.
 - ⁶ If abnormal, run full thyroid panel, including Free T3 and Total T4.
 - ⁷ Subsequent Courses (after the first course) will receive MDX-010 every 3 weeks X 4 if the patient is stable or has a partial or mixed response with toxicities of grade 1 or less after the 1st course. Subsequent courses for patients with stable, partial or mixed response, or for patients with complete or partial responses that have relapsed, may be offered.
- ** Additional ophthalmologic exams will be performed if the patient experiences ocular symptoms.

3.6 Off Study Criteria:

Patients may be removed from the study in the following situations:

- Protocol violations
- Disease progression
- Subject withdrew consent
- Lost to follow up
- Death

Medarex reserves the right to discontinue any study for administrative reasons at any time. If appropriate, reimbursement for reasonable expenses will be made. Authorized physicians must notify ORKAND when a patient is taken off study.

3.7 Post Study Evaluation (Follow up):

Patients will undergo physical examination, including vital signs, blood sampling for hematological and biochemical evaluation and, as clinically indicated, chest radiography, pulmonary function, diagnostic imaging, three weeks following the last treatment, then at three month intervals for 1 year, at 6 month intervals for two years, and then at 12 month intervals or until disease progresses. Prior to termination of participation in the study, each patient will undergo physical examination, diagnostic imaging, and blood sampling for hematological, biochemical, and immune function assessments.

4.0 Supportive Care

Concomitant medications to control side effects of therapy will be given if patients have documented symptoms. Meperidine (25-50 mg) will be given intravenously if severe chilling develops. Other supportive therapy will be given as required. If patients require systemic steroid therapy they will be taken off treatment.

4.1 Acute hypersensitivity

Acute hypersensitivity reactions to MDX-010 antibody should be managed as outlined below.

- For mild symptoms: (Localized cutaneous reactions such as mild pruritis, flushing, or rash.) Decrease the rate of infusion until recovery from symptoms, remain at bedside and monitor patient; complete MDX-010 antibody infusion at the initial planned rate. Diphenhydramine 50 mg, may be administered at the discretion of the treating physician.
- For moderate symptoms: (Any symptom not listed above (mild symptoms) or below (severe symptoms) such as generalized pruritis, flushing, rash, dyspnea, or hypotension with systolic BP >80 mmHg.) Interrupt MDX-010 antibody infusion, administer diphenhydramine 50 mg i.v., remain at bedside and monitor patient until resolution of symptoms. Corticosteroids may abrogate any immune response, but may be administered at the discretion of the treating physician. If systemic steroid therapy was not needed, then at the discretion of the treating physician, MDX-010 infusion may be resumed after recovery of symptoms. At the discretion of the treating physician, MDX-010 antibody infusion may be resumed at one half the initial infusion rate, then increased incrementally to the initial infusion rate. If symptoms develop after resumption of the infusion, the infusion should be discontinued and no additional MDX-010 should be administered. At the discretion of the treating physician, additional oral or i.v. antihistamine may be administered.
- For severe symptoms: (Any reaction such as life threatening bronchospasm, systolic blood pressure <80 mm Hg, or angioedema.) Immediately discontinue infusion of MDX-010 and initiate appropriate therapy (potentially to include epinephrine 1 mg i.v. or subcutaneously and/or diphenhydramine 50 mg i.v. or solumedrol 100 mg i.v.) as needed. Monitor patient until resolution of symptoms. No further MDX-010 will be administered.

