3.3.1 MDX-010

There will be no intra-patient dose modifications of MDX-010. Patients will discontinue treatment with MDX-010 if they experience an adverse event felt to be possibly or probably related to MDX-010 antibody that meets the following criteria:

- A patient who requires systemic steroid therapy for any reason will not receive further treatment with MDX-010 but will be followed until off study criteria are met.
- Any infusion related reaction of \geq grade 3. Infusion related reactions are defined as acute reactions that develop and resolve within 48 hours of the start of an infusion. This includes reactions that are responsive to therapy within that time frame except for Grade 3 fever that resolves within 48 hours. Exclusions to discontinuing therapy will be made in the presence of an objective response when the toxicity resolves prior to the next infusion.
- Any autoimmune toxicity of $>$ grade 2 that has the potential to be life threatening with continued antibody administration and is not associated with a potential therapeutic response, except rash, vitiligo or asymptomatic autoantibody detection. An autoimmune reaction is defined as an inflammatory process that compromises the function of any organ and is not attributable to another etiology.
- Any autoimmune toxicity (any grade) that does not resolve by the time that additional dosing with MDX-010 is considered. Patients may delay subsequent doses in a course by up to a maximum of 3 weeks while awaiting resolution of an autoimmune toxicity.
- Uveitis or episcleritis that is symptomatic (causing eye pain, photosensitivity, or blurred vision)
- Exclusions to these criteria include inflammation of $<$ grade 4 that is attributable to a local anti-tumor reaction that could potentially be a therapeutic response. This

includes inflammatory reactions at the site of tumor resection or in draining lymph nodes, or in sites suspicious for metastasis.

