4.4 Treatment of \geq Grade III Non-autoimmune-mediated Adverse Events

Treatment for any \geq Grade III adverse event not felt to be due to an autoimmune process may be treated as clinically indicated. No further doses of MDX-010 will be given once a patient experiences a non-skin-related \geq Grade III adverse event attributable to the investigational agents.

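### Protocol 4.1 sorts acute hypersensitivity by symptom without a grade, so a grade 3 reaction that Section 3.2 makes a permanent stop can be read as moderate and the infusion resumed

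*Protocol*

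**What the plan says.** Four places in the protocol bear on whether MDX-010 continues after an acute reaction.

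- **Section 3.2 (Drug Administration)** sets a stop by grade. The threshold is grade 3 or higher: "Grade 3 bronchospasm or other hypersensitivity reaction occurs, the infusion should be discontinued and no additional MDX-010 should be administered". It has no exception.
- **Section 4.1 (Acute hypersensitivity)** sets out mild, moderate and severe groups by symptom. Moderate is "Any symptom not listed above (mild symptoms) or below (severe symptoms) such as generalized pruritis, flushing, rash, dyspnea", or hypotension with systolic pressure above 80 mmHg. For this group the infusion is interrupted and the patient is watched at the bedside until symptoms resolve. If systemic steroids were not needed, "MDX-010 infusion may be resumed after recovery of symptoms" at the physician's discretion. Severe is "Any reaction such as life threatening bronchospasm, systolic blood pressure <80 mm Hg, or angioedema", and for that group MDX-010 ends.
- **Section 3.3.1 (MDX-010)** discontinues treatment after an infusion-related reaction of grade 3 or higher, "except for Grade 3 fever that resolves within 48 hours". It then adds: "Exclusions to discontinuing therapy will be made in the presence of an objective response when the toxicity resolves prior to the next infusion".
- **Section 4.4** (grade III or higher events not thought to be autoimmune) says "No further doses of MDX-010 will be given once a patient experiences a non-skin-related" event of that grade attributable to the study agent.

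The SAP does not address the matter. Its Section 5.10 reports no clinical response in the first stage and termination of the trial.

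**The concern.** Section 4.1 is the text a physician would follow during a reaction, and it is the only one of the four that uses no grade. It names bronchospasm as severe only when life threatening, and it places in the moderate group whatever is not listed elsewhere. A physician who applies those steps literally could restart the infusion in a patient whom 3.2 bars from any more MDX-010.

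What is at stake is re-exposure to the antibody after a serious reaction; Section 5.4 counts an infusion event of grade 3 or higher as a serious adverse event. There would also be a slight effect on the exposure summary in SAP 5.6.

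**Working it through.** No arithmetic applies: neither rule rests on a rate, a power or a sample size. The check is to take particular reactions through the sections and compare the instructions.

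| Reaction | Section 3.2 | Section 4.1 |
|---|---|---|
| Life-threatening bronchospasm | Permanent stop | Severe: permanent stop |
| Grade 3 bronchospasm, not life threatening | Permanent stop | Not named as severe; fits moderate, so resumption is possible |
| Generalized rash or pruritis of grade 3, as a hypersensitivity reaction | Permanent stop | Named as moderate with no upper limit; resumption is possible |
| Grade 3 dyspnea, or grade 3 hypotension above 80 mmHg systolic, as a hypersensitivity reaction | Permanent stop | Named as moderate with no upper limit; resumption is possible |

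The sections agree in the first row and can part in the other three.

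**Can a grade 3 reaction fall short of life threatening?** The general definitions in Section 7.4 put severe at grade 3 and life threatening or disabling at grade 4. They apply only to events outside CTC AE 3.0, and that scale is not in the documents, so for bronchospasm this is an assumption. The skin example has some support in the protocol itself: Section 4.3 treats severe generalized pruritis or rash as grade III or higher. That section concerns autoimmune events, but it shows that the protocol grades these symptoms that high.

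**Does the open severe list settle the matter?** Not fully. Severe is introduced by examples, so an unlisted grade 3 reaction may belong there. Moderate is defined as what is not listed as mild or severe, so the same reaction also fits moderate. The two groups lead to opposite outcomes.

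**Do the other sections close the gap?**

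- Section 4.4 covers only events that are not skin related, and it speaks of further doses, not of the infusion in progress.
- Section 3.3.1 does stop treatment at grade 3 or higher, but with exceptions, and 4.1 does not refer to it on this point.

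**The exception in 3.3.1.** That section defines infusion-related reactions as acute ones that develop and resolve within 48 hours of the start of an infusion. A grade 3 hypersensitivity reaction can meet this definition. For a patient with an objective response whose reaction resolves before the next infusion, 3.3.1 lets treatment continue and 3.2 forbids it. This second inconsistency does not depend on how 4.1 is read.

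**The case against.** The strongest reply is that the protocol, read as a whole, already bars the outcome. Section 3.2 is explicit and specific; 4.1 only permits resumption and never orders it, and a permission in supportive-care text does not displace a prohibition elsewhere. The severe list is open, and the general scale in 7.4 uses moderate for grade 2 and severe for grade 3, so the natural reading puts a grade 3 reaction under severe. Section 3.3.1 points the same way, as does 4.4 for bronchospasm. The moderate path also has safeguards beyond interruption and monitoring: "If symptoms develop after resumption of the infusion, the infusion should be discontinued and no additional MDX-010 should be administered".

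Much of this stands. A reader might infer that 3.2 and 4.1 give contradictory orders. The documents do not support that: a physician can comply with both by stopping, and a careful reader of the whole protocol probably would.

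What the reply does not remove is the overlap in 4.1 and the missing pointer to 3.2. The safeguard against a second reaction acts only after the patient has been re-exposed. It is also fair to say that the 3.3.1 exception had no occasion to operate through stage one, since SAP 5.10 reports no clinical response. That limits its consequence in this trial but does not reconcile the text.

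**Conclusion.** The point holds as a minor wording fault affecting patient safety. Section 4.1 can be read to let the infusion resume after a grade 3 reaction for which 3.2 ends MDX-010, and the responder exception in 3.3.1 conflicts with 3.2.

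Its size cannot be put as a number. The documents give no rate of such reactions and no count of patients treated. Re-exposures would in any case be fewer than reactions, because resuming is optional and is ruled out if systemic steroids were needed.

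Two further inferences should be resisted. Nothing in the documents shows that any patient was actually resumed after a grade 3 reaction. Nor does the ambiguity bear on the response decision: the stage-one rule counts responders among 21 patients and is the same under either reading.

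The conclusion rests on two assumptions:

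- For the bronchospasm example, CTC AE 3.0 allows a grade 3 event that is not life threatening.
- The supplied protocol, dated March 24, 2005, is the text that applied. SAP Table 2 cites a protocol section 2.2.7 C that this version lacks, so a later version may exist, and its Section 4.1 may differ.

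**What to change.** Add to Section 4.1:

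> Any hypersensitivity reaction of CTC AE 3.0 grade 3 or higher is managed as severe under Section 3.2: stop the infusion and give no further MDX-010; the option to resume applies only below grade 3.

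Add to Section 3.3.1:

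> The objective-response exception does not apply to hypersensitivity reactions covered by Section 3.2.

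Keep the events already named as severe in 4.1.

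The cost is two sentences, with no added procedures, patients or data and no change to the analysis. Because the trial has been terminated, the change matters mainly wherever this protocol text remains in use or is carried into another study.
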